T1D Risk Determination: While TrialNet and the larger T1D community successfully used staging to help patients, providers, and regulatory agencies understand the natural history of pre-clinical T1D, TrialNet and other prospective longitudinal studies^{12,30,31}, as introduced above, now able to more precisely define populations at risk for developing Stage 3. Specifically, using TrialNet OGTT data we identified markers defining cohorts with a 2-year 50% risk of progressing to Stage 3 T1D. Based on these analyses, 2-yr High-Risk (50% risk for progression to Stage 3 T1D) criteria were defined as ever having two or more T1D-associated islet autoantibodies, ADA Stage 2 criteria (dysglycemia defined as impaired fasting plasma glucose of \geq 100 mg/dL (\geq 5.6 mmol/L), impaired glucose tolerance (a 2-h plasma glucose of \geq 140 mg/dL (\geq 7.8 mmol/L), or high glucose levels at intermediate time OGTT points (30, 60, 90 min levels of \geq 200 mg/dL [\geq 11.1 mmol/L]) and meeting at least 1 of the following characteristics on one visit: HbA1c \geq 5.7% and < 6.5% or Index60 \geq 1.4 or DPTRS \geq 7.4^{12,30,31}.

To reiterate, while staging inherently predicts progression to disease (e.g. Stage 2 broadly provides a 5 year 50% progression risk), the use of additional risk markers routinely obtained during TrialNet OGTTs identifies sub-populations with even greater short term (2-year 50%) risk of progression to Stage 3 T1D. These highest risk participants are optimal for studies in prevention / delay as studies

in this space rely on event rates of individuals progressing to Stage 3 T1D rather than a time related endpoint (e.g. 1 year post treatment)³². As such, this protocol acknowledges and uses staging but goes further to rely on additional risk markers to define a study population of participants with a 2 year 50% risk of progression.

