3.3 Treatment Assignment and Double Masking

Participants who have provided consent and meet eligibility criteria will be randomized to one of the two arms. The randomization will be stratified by age (< 18 and ≥ 18). The participants will not be informed regarding the intervention assignment until the end of the study. The investigator and clinic personnel will also be masked as to study assignment. Laboratories performing assays for this protocol will be masked as to the identity of biological material to be studied.

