The TrialNet Eligibility and Events Committee will review and adjudicate any cases with only a single objective measure, cases which do not meet the criteria above, and/or cases which have uncertain results of tests and/or the test procedures. Qualifying glucose values should be from laboratory tests, rather than capillary blood glucose meter readings.

The study design is a 2:1 randomized, double-blind placebo-controlled trial. The primary objective of this trial is to assess the efficacy of ATG versus placebo control in terms of the risk of diabetes onset in this target population as defined by the eligibility criteria.

The cumulative incidence of diabetes onset over time since randomization within each treatment group will be estimated using the Kaplan-Meier method (proportion surviving diabetes-free as a function of time). The difference between groups in the cumulative incidence functions, and the associated hazard functions, will be tested at the 0.05 level, two-sided, using the Cox Proportional Hazards (PH) model, adjusted for age. Assumptions of proportionality will be tested, and if that assumption does not hold, then alternative analytic approaches will be used to allow for time-varying coefficients in the model. The relative risk of diabetes onset between groups will be estimated from the Cox regression model. The critical values will be determined by the group-sequential procedure outlined in the section entitled Interim Monitoring Plan below.

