8.2 Secondary Outcome and Analyses

A variety of secondary analyses are planned, some of which will include the following :

- Subgroup analyses may be conducted comparing the effects of low-dose ATG versus control on the risk of diabetes within subsets of the study cohort. Subgroups of the population may be classified by age, gender, race/ethnicity, specific antibody status at baseline, and HLA status (e.g. presence or absence of HLA DR3/DQ2 and/or HLA DR4/DQ8). Differences in the treatment effect between subgroups will be tested using a covariate by treatment group interaction term in the Cox regression model.
- The heterogeneity of treatment effect across categorical factors will be assessed through a covariate by treatment group interaction in a Cox hazards regression model. These factors include gender, race/ethnicity, specific antibody status at baseline and HLA status (i.e. presence or absence of HLA DR3/DQ2 and/or HLA DR4/DQ8).
- Similarly, subset analyses will be conducted using the values of quantitative baseline factors (dichotomized at the median) Including weight, BMI-Z, CBC and the immunologic and metabolic factors described in Section 5 that include autoantibody titers, basal c-peptide, OGTT stimulated c-peptide (peak and AUC-mean).
- Additional covariates may be defined during the conduct of the study. The reporting

of the analyses will distinguish between factors specified prior to primary analysis and those identified post-hoc during analysis.

- Longitudinal analyses will assess the effects of low-dose ATG versus control treatment on immunologic and metabolic markers over time up and following progression to stage 3 T1D. Differences between groups in the mean levels of quantitative factors over time will be assessed using a normal errors linear model for repeated measures. Differences between groups in the prevalence of qualitative factors over time will be assessed using generalized estimating equations for categorical measures. Generalized estimating equations may also be employed for the analysis of quantitative factors when the normal errors assumptions are violated.

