8.4 Sample Size and Power Calculations

This study has been designed to provide at least 85% power to detect a 60% risk reduction in the hazard rate for progression from Stage 2 (with a 50% 2 year progression risk) to Stage 3 T1D using a two-sided test at the 0.05 level once the targeted number of Stage 3 T1D's have been observed. We note that if accrual is more rapid than expected, minimum follow-up on participants may need to be extended or additional accrual in order to meet the number of events required for the final analysis.

A total of 101 participants will be randomized in a 2:1 allocation to treatment with low-dose ATG vs. placebo (e.g., 68 and 33, respectively). Randomization will be conducted using block randomization with variable block sizes.

The assumptions underlying the estimated sample size for this design are: (1) a detectable hazard ratio of 0.4, (2) a minimum of 2 years of follow-up on all participants who have not progressed to Stage 3 T1D, (3) an accrual period of approximately 4 years, and (4) less than a 10% two-year dropout rate in both groups. Under the above assumptions, the target total number of events is equal to 44 assuming the alternative hypothesis; i.e., the final analysis will be conducted once 44 events (Stage 3 T1D diagnosis) have been observed.

With this augmented eligibility criteria and based on the TrialNet Pathway to Prevention (PTP) data (TN01), we would expect to have on average 20 participants per year aged 6 to 35 years old identified with two or more of the high-risk features described in the eligibility criteria.

The final test of significance will employ group sequential critical values to protect against inflation in the type I error probability due to interim assessments of the emerging data for review by the DSMB (see Section 8.5).

Note the accrual period and the study sample are only projections, and the actual accrual rate and the loss-to-follow-up rate are unknown. As the study progresses, more accurate projections of the study end date will be computed based on the observed rate of enrollment, the observed number of events, and the observed rate of loss-to-follow-up. These data will be provided to the DSMB and the TrialNet governing body, and if need be, this document will be amended to reflect revised planning parameters.

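### The primary Cox model adjusts for age only and leaves out the continuous risk scores measured at entry: the test is valid, but it may give up power

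*Combined protocol and SAP*

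**What the plan says.** Section 8.1 specifies that the arms will be compared, and the difference "tested at the 0.05 level, two-sided, using the Cox Proportional Hazards (PH) model, adjusted for age". Age is the only covariate named. It is also the only randomization factor: Section 3.3 says "The randomization will be stratified by age", with a cut at 18 years.

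Section 2.2 presents the metabolic markers as prognostic for Stage 3. It says that "the use of additional risk markers routinely obtained during TrialNet OGTTs identifies sub-populations with even greater short term (2-year 50%) risk", and it puts two-year progression in Stage 2 overall at 30%. Section 3.1.1 requires OGTT-defined dysglycemia plus at least one of HbA1c, Index60 or DPTRS at the same visit, within 52 days of randomization. Both scores are computed from OGTT glucose and C-peptide. DPTRS also uses BMI and age; Index60 has no age term.

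Section 8.4 sizes the trial for "at least 85% power to detect a 60% risk reduction in the hazard rate" in a population "with a 50% 2 year progression risk", "using a two-sided test at the 0.05 level". It lists "a detectable hazard ratio of 0.4" among its assumptions and does not say whether this ratio is crude, age-adjusted or conditional on the scores.

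**The concern.** In a Cox model, leaving out a covariate that predicts the event moves the treatment hazard ratio toward 1, even when randomization balances that covariate. The standard error shrinks only slightly in return, so power falls relative to a model that includes it.

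Here the omitted covariates are the ones used to define the trial population. Eligibility is met by any one of three markers, and Index60 and DPTRS have floors but no ceilings. A participant can also qualify on HbA1c with low scores. Risk may therefore still vary with the scores among those enrolled. Section 8.4 expects about 20 eligible people per year, so power lost in the analysis would be slow to recover by enrolling more. The secondary C-peptide model in Section 8.2 does adjust for a baseline metabolic measure; the primary model does not, and no reason is given.

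**Working it through.** **Inputs from the documents.** Two-sided 0.05; power 85%; hazard ratio 0.4; control risk 50% at two years; 68 and 33 participants; 44 events; accrual about 4 years; dropout below 10% over two years (Section 8.4). The final boundary is chi-square 3.88, p = 0.0489 (Section 8.5.2); z = 1.969 was used.

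**Assumed, because the documents do not give it.** The SD of the log hazard among enrolled participants that age does not explain was varied from 0 to 1.0. An SD of 0.5 means a hazard ratio of exp(0.5) = 1.65 per SD of risk, and 1.0 means 2.72. The age effect was given an SD of 0.3 on the log hazard.

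**Step 1: the plan's own figure.** Control hazard = ln 2 / 2 = 0.347 per year. Dropout hazard = -ln(0.9) / 2 = 0.0527 per year.
- Schoenfeld with the 2:1 allocation: (1.960 + 1.036)² / [(2/9)(ln 0.4)²] = 8.98 / 0.187 = 48.1, so 49 events. Power at 44 events is 81.7%.
- Using the event split expected under the alternative (about 53.5% in the ATG arm): 8.98 / [(0.535)(0.465)(0.840)] = 43 events. Power at 44 is 85.8%.
- Cox simulation of the design, cut at the 44th event, with no residual risk: 84.4%.

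The stated 44 events and 85% therefore reproduce when the event split under the alternative is used.

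**Step 2: how strong the markers are.** Stage 2 overall: -ln(0.70) / 2 = 0.178 per year. Marker-defined group: 0.347 per year. The ratio is 1.9. This contrasts two populations; it does not give the spread within the trial.

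**Step 3: power at 44 events, conditional hazard ratio 0.4, control two-year risk held at 50%.** There were 4,000 trials per setting, with Monte Carlo error about 0.6 points. In this table the score captures all the residual risk.

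| Residual SD | Age only | Age + score | Gain (points) |
|---|---|---|---|
| 0 | 84.4% | 83.7% | -0.7 |
| 0.25 | 82.2% | 83.0% | 0.8 |
| 0.5 | 77.9% | 83.3% | 5.4 |
| 0.75 | 71.2% | 82.7% | 11.5 |
| 1.0 | 62.3% | 82.2% | 19.9 |

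The average age-only hazard ratio drifts to about 0.43, 0.45 and 0.49 at SD 0.5, 0.75 and 1.0.

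Hand check at SD 0.75, from the simulated average hazard ratio and standard error:
- Age only: -ln(0.453) / 0.313 = 2.53; 2.53 - 1.969 = 0.56, so power is about 71%.
- Age + score: -ln(0.389) / 0.322 = 2.93; 2.93 - 1.969 = 0.96, so power is about 83%.

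**Step 4: the score captures half the residual variance.**

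| Residual SD | Age only | Age + score | Gain (points) |
|---|---|---|---|
| 0.5 | 78.1% | 80.7% | 2.6 |
| 0.75 | 70.8% | 75.8% | 5.0 |
| 1.0 | 62.4% | 70.4% | 8.0 |

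**Step 5: 0.4 read as the age-only hazard ratio.** The conditional ratio was set to 0.37 at SD 0.5 and 0.335 at SD 0.75, so that the age-only ratio came out near 0.40. Power is then 83.6% against 88.8% at SD 0.5, and 84.9% against 93.5% at SD 0.75.

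**Step 6: no treatment effect.** Type I error is 5.1 to 5.4% with age only and 5.4% with age plus one score. With three covariates added to age it is about 6%, a reason to add only one.

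**The case against.** The strongest reply is that nothing in Section 8.1 is wrong. The test holds its level, the covariate matches the stratification factor, and the 85% may already refer to the age-adjusted hazard ratio. In that case no planned power is lost and adjustment is only an unused gain. Age may also carry part of the information: the protocol says children progress faster, and age is a term in DPTRS. The entry thresholds may narrow the spread of the scores. All of this stands, and it is why the size is shown as a range that starts at no loss.

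Four stronger readings are tempting, and the documents do not support them.
- A reader might infer that power is lost whenever baseline risk varies. Variation that age explains costs nothing, and at residual SD 0.25 the difference is about 1 point.
- A reader might take the rise from 30% to 50% as proof of wide variation within the trial. It compares Stage 2 overall with the selected group.
- A reader might infer that chance imbalance in a score biases the test. Over repeated randomization, that imbalance is already part of the test's error rate.
- A reader might infer that Section 8.2 wastes the same scores through median splits. That list names weight, BMI-Z, CBC, autoantibody titers and C-peptide measures, not Index60 or DPTRS, and the section separately plans group-by-covariate interactions in Cox models.

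Nor is the stratification handled wrongly: age is the only stratum and age is in the model.

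**Conclusion.** The concern holds as a missed efficiency. The primary analysis omits prognostic scores that should be available for nearly everyone at entry. Adding one never costs as much as 1 point in the settings examined, and it could gain anything from nothing to about 20 points. The top of that range needs a residual SD of 1.0 and a score that captures all of it; with half captured, the gain is about 3 to 8 points for SD 0.5 to 1.0. The direction is the same under either reading of the hazard ratio of 0.4.

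Confidence is high on what the model contains and on the direction. It is moderate at most on the size, because the residual SD is assumed. The simulations also assume proportional hazards and a log-linear score effect, and they apply the final boundary without stopping at the interim.

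**What to change.** In Section 8.1, name one continuous baseline score from the qualifying OGTT as a covariate alongside age in the primary Cox model. Index60 is a natural candidate because it has no age term. Fix the choice before unblinding, use the same model at the 22-event interim analysis, and state what is done if a score is missing. Report the age-only model as a sensitivity analysis. One score is preferable to three with only 44 events.

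The cost is a change of wording; no new data are needed. The reported hazard ratio becomes conditional on the score, which the report should say. If the score proves uninformative, power falls by less than 1 point. Before choosing, the sponsor could estimate the spread of risk by score from the TrialNet Pathway to Prevention data, applying this trial's entry criteria, which would replace the assumed range with a figure.

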8.5.2 Formal Interim Analysis

A formal interim analysis of efficacy will be conducted when 50% of events (i.e., information fraction = 0.50) have been observed; i.e., we will conduct an interim analysis to compare the two treatment arms when 22 participants enrolled on this trial have a reported progression to Stage 3 T1D. To preserve the Type I error rate control for each of these comparisons on superiority, the Lan-DeMets error spending rate function with the O'Brien-Fleming boundaries is utilized. If these boundaries are crossed, then the TrialNet DSMB will determine if accrual to that arm should be suspended and/or if treatment of participants should be modified based on these results. These computations as based on Reboussin et al paper⁷³.

Information fraction	Cumulative events	Alpha (in terms of the efficacy boundary)	Chi-square Efficacy Boundary* (p-value)
0.50	22	0.00153	8.78 (0.00305)
1.00	44	0.0235	3.88 (0.0489)

* ATG superior direction only

In lieu of a formal futility rule at the interim analysis, we will utilize conditional probability methods to assess the probability that low-dose ATG will delay time to T1D based on the data observed

(i.e., 50% information). The DSMB will also consider early termination due to absence of a treatment effect based on computations of conditional power conducted under the initial study design. Conditional probabilities of ≤ 0.2 will be considered strong evidence for early termination.

While the study is proposed to investigate whether treatment with ATG will lead to a reduction in the rate of progression to Stage 3 disease, the design incorporates the question of whether there is a difference in the rate of progression in either direction, i.e., an increase or decrease. The target sample size is based upon a 2-sided test of significance at the 0.05 level to ensure that the study would have 85% power to detect the minimally clinically defined difference in either direction should it occur.

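### Section 8.1 lets a proportional-hazards check move the primary analysis to an unspecified time-varying model; if that model replaces the Cox test, type I error can rise from about 5% to between 7% and 10%.

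*Combined protocol and SAP*

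**What the plan says.** Section 8.1 states that the difference between arms "will be tested at the 0.05 level, two-sided, using the Cox Proportional Hazards (PH) model, adjusted for age". A check of the model is then planned: "Assumptions of proportionality will be tested". The paragraph also says what follows from a failed check: "if that assumption does not hold, then alternative analytic approaches will be used to allow for time-varying coefficients in the model". The sentences after that say that the relative risk will come from the Cox regression and that "The critical values will be determined by the group-sequential procedure outlined in the section entitled Interim Monitoring Plan below".

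Section 8.5.2 supplies those values in a table column headed "Chi-square Efficacy Boundary* (p-value": 8.78 (0.00305) at 22 events and 3.88 (0.0489) at 44 events.

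The plan does not state:
- which proportionality test is used, or at what level;
- which terms it covers (treatment, age or both);
- the time function for the varying coefficient;
- the hypothesis, degrees of freedom and critical value after a switch;
- whether the time-varying analysis decides the trial or only describes how the effect changes.

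**The concern.** The fallback sits inside the primary-analysis paragraph and carries no label such as supportive or exploratory, so replacing the Cox test is a natural reading. On that reading the data choose the confirmatory test.

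When treatment does nothing, the trials that fail the proportionality check are those where chance produced a strong treatment-by-time pattern. A joint test of treatment and treatment-by-time then counts that same chance pattern again, so it rejects far more often than 5% in the trials that reach it.

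Two things are at stake. One is the 0.05 level, which the group-sequential plan is there to protect. The other is having a single rule for whether ATG worked. The interim correction moves the final p-value only from 0.05 to 0.0489, whereas an uncontrolled switch can add roughly 2 to 5 percentage points.

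**Working it through.** **Inputs from the plan.** Two-sided 0.05; 22 and 44 events (8.5.2). From 8.4: "designed to provide at least 85% power to detect a 60% risk reduction in the hazard rate", "progression from Stage 2 (with a 50% 2 year progression risk) to Stage 3 T1D", and "A total of 101 participants will be randomized in a 2:1 allocation to treatment with low-dose ATG vs. placebo (e.g., 68 and 33, respectively"; accrual of about 4 years, at least 2 years of follow-up, dropout below 10% over two years.

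**Assumptions not in the plan.** Pre-test level 0.05 or 0.10; time functions t, log t and rank; early/late split points; exponential event times; uniform accrual. Age was not in the simulation.

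**1. The plan's own figures reproduce.**
- Events: D = (1.960 + 1.036)² / [p(1 − p)(ln 0.4)²], where p is the share of events on ATG under the alternative. With p ≈ 0.54, D = 8.98 / (0.248 × 0.840) ≈ 43.1, so 44. Power at 44 events is 85.7–85.8%.
- Boundaries: Lan-DeMets spending of O'Brien-Fleming type at one-sided 0.025 and information 0.5 spends 0.001525. That gives z = 2.963, chi-square 8.78, p = 0.00305. The final z is 1.969, chi-square 3.875, p = 0.0490, which matches the table up to rounding.

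**2. The boundaries are 1-df values.** On 1 df, 8.78 and 3.88 have p = 0.00305 and 0.0489. On 2 df they have p = 0.0124 and 0.144.

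**3. Type I error after a switch, asymptotically.** Under the null, the Cox statistic Q₁ and the proportionality statistic Q₂ are independent chi-squares on 1 df, and the 2-df joint statistic is Q₁ + Q₂. With pre-test level a and cut-off k (the 1 − a quantile of a 1-df chi-square):

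error = (1 − a) × P(Q₁ > c₁) + P(Q₂ > k and Q₁ + Q₂ > c₂)

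| Pre-test | Cut-offs c₁, c₂ | No switch | Switch | Total |
|---|---|---|---|---|
| 0.05 | 3.84, 5.99 | 0.95 × 0.05 = 0.0475 | 0.0249 | 7.2% |
| 0.05 | 3.88, 3.88 | 0.95 × 0.0489 = 0.0464 | 0.0499 | 9.6% |
| 0.10 | 3.84, 5.99 | 0.90 × 0.05 = 0.0450 | 0.0297 | 7.5% |
| 0.10 | 3.88, 3.88 | 0.90 × 0.0489 = 0.0440 | 0.0719 | 11.6% |

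In the first row, a true null is rejected in 0.0249 / 0.05 ≈ 50% of the trials that switch. In the second row it is 0.0499 / 0.05, almost all of them.

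**4. Simulation check.** 40,000 null trials, 68:33, analysed at 44 events.

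| Decision rule | Pre-test 0.05 | Pre-test 0.10 |
|---|---|---|
| Cox test always, no switch | 4.7% (Wald) to 5.0% (likelihood ratio) | same |
| 2-df joint test at its own critical value, likelihood ratio | 7.2–7.3% | 7.6% |
| Same, Wald | 5.9–6.4% | 6.5% (one time function) |
| 2-df statistic against the 1-df cut-off | 9.3–9.7% | about 12% |
| Early or late coefficient significant | 6.1–7.4% | 6.5–8.5% |
| 1-df average log hazard ratio | 4.8% | 4.8% |

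Adding the 22-event look, with the switch allowed only at the final analysis, changes these by about 0.1 point. Allowing the switch at both looks takes the 2-df statistic against the 1-df cut-off to 9.7–10.3% at a 0.05 pre-test. A 2-df test used in every trial has simulated size 5.4%, so most of the inflation comes from the data-driven choice and not from the 2-df test itself.

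**The case against.** The strongest reply is that the plan never says the confirmatory test changes. Allowing for time-varying coefficients may mean only describing how the effect evolves. The sentences on relative risk and critical values still point to the Cox model and the 1-df table. On that reading the error is about 5%, and a 1-df average effect from the time-varying model gives 4.8%. The check might also flag age and not treatment. A time-varying age term leaves treatment on 1 df and should not inflate its test (reasoned, not simulated). All of this stands. It shows that harmless readings exist, but the plan does not choose one.

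Three stronger readings are tempting and are not supported:
- **That the plan as written has a definite inflated error, say 8–9%.** Any single figure needs a pre-test level, a time function and a decision rule that the plan does not give. For the plainest replacement, a 2-df joint test, the figure is about 7%. Values near 8% arise from an early-or-late rule (7.8–8.1% asymptotically at a 0.05 pre-test), which the plan does not mention.
- **That the printed boundaries fail after any switch.** They fail only when treatment carries more than one degree of freedom. They still fit a 1-df contrast.
- **That waning of a two-infusion course makes the inflation likely.** A switch caused by real waning happens when there is an effect, so it says nothing about error under the null. Section 2.3 in fact reports benefits lasting beyond 2 years, although section 2.3.1 describes CD8 counts recovering within about 2 months.

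**Conclusion.** The concern holds in conditional form. Section 8.1 contains a data-driven switch with an undefined endpoint. If the fallback replaces the Cox test, the type I error is about 7% for a 2-df joint test at its own critical value. It is about 9.6% if the 2-df statistic is compared with 3.88, the only final critical value the plan prints. Both figures assume a 0.05 pre-test; a 0.10 pre-test takes the second to about 12%. If the fallback is a 1-df average effect, descriptive only, or confined to the age term, the error stays near 5%.

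The results rest on the assumptions listed in the working, on simulations without the age covariate, and on large-sample independence of the Cox and proportionality statistics. At 44 events the Wald form of the joint test inflates less (5.9–6.4%). This is more than missing detail, because the rule that decides the trial differs between readings and most readings that replace the Cox test exceed 5%.

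**What to change.** Replace the fallback sentence in section 8.1 with one to this effect: the age-adjusted 1-df Cox test of treatment, judged against the section 8.5.2 boundaries, is the confirmatory test whatever the proportionality check shows. Time-varying hazard ratios and, for example, Kaplan-Meier differences at a stated time or restricted mean diabetes-free time are supportive and do not change the primary decision. Make the change before any unblinded look.

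No switch is needed for validity. The unadjusted 1-df score (log-rank) test holds its level under no treatment effect without assuming proportional hazards under the alternative. Randomisation should make the age-adjusted version close to this, although that was not simulated.

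The cost is one sentence. The 101 participants, the 44 events and both boundaries stay as they are. Under marked non-proportionality the hazard ratio has to be read as an average effect, and the test may lose some power. The supportive estimates would then show how the effect changes over time.
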